### 7.2.1. Duvelisib Dosing Modifications and Discontinuation

As described in [Table 4](#) and in [Section 7.2.1.1](#) (treatment hold for hematologic toxicities) and [Section 7.2.1.2](#) (treatment hold for nonhematologic toxicities), duvelisib should be held upon the first occurrence of certain toxicities. Upon resolution of the AE, duvelisib treatment should be reinitiated at the current dose level according to the guidelines in [Table 4](#). On subsequent occurrences of the same event, duvelisib should be reinitiated at 1 dose level lower than current dose level (see [Table 5](#)). Duvelisib may be held up to 42 days because of treatment-related AEs. Doses held for > 42 days because of treatment-related AEs will result in permanent discontinuation from duvelisib. Any subject who requires a dose-level reduction to below 10 mg BID because of treatment-related AEs will be permanently discontinued from duvelisib treatment.

Subjects who discontinue duvelisib should return to the clinic for the TT Visit assessments and may continue to be followed for OS based on the length of survival follow-up defined in the subject's previous study.

Dose levels for duvelisib are shown in [Table 5](#).

**Table 5: Duvelisib Dose Levels**

| Starting Dose | Dose Level -1 | Dose Level -2 |
|---------------|---------------|---------------|
| 75 mg BID     | 50 mg BID     | 25 mg BID     |
| 50 mg BID     | 25 mg BID     | 15 mg BID     |
| 25 mg BID     | 15 mg BID     | 10 mg BID     |
| 15 mg BID     | 10 mg BID     | NA            |

Abbreviations: BID = twice a day; NA = not applicable.

Note: No dosing below 10 mg BID is allowed.

Subjects who have a dose reduction because of a toxicity may be eligible for a dose increase back to the dose level before the reduction (ie, the starting dose level or dose level of previous reduction if subject's dose was reduced more than 1 level) if the following criteria are met:

- Subject has tolerated the lower dose level for > 1 treatment cycle
- Subject has recovered to baseline levels from the toxicity that caused the dose reduction

#### 7.2.1.1. Treatment Hold for Hematologic Toxicity

Treatment with duvelisib should be held for the following symptomatic hematologic toxicities:

- Grade 3 or higher febrile neutropenia
- Grade 3 or higher thrombocytopenia associated with Grade 2 or higher hemorrhage

The subject should be reevaluated at least weekly until the toxicity improves according to the guidelines in [Table 4](#).

Subjects experiencing Grade 4 hematologic toxicities other than febrile neutropenia or thrombocytopenia with hemorrhage may continue on their current dosage of duvelisib at the discretion of the Investigator.

#### 7.2.1.2. Treatment Hold for Nonhematologic Toxicity

Treatment with duvelisib should be held for Grade 2 or higher pneumonitis/pneumonia or Grade 3 or higher other nonhematologic toxicities:

- Grade 2 or higher pneumonitis/pneumonia, defined as symptomatic and requiring medical intervention, including oral antimicrobials and/or steroids:
  - New onset or worsening of cough, shortness of breath, hypoxia, or new radiographic findings should be evaluated for pneumonitis. If pneumonitis is suspected, duvelisib should be held, and administration of corticosteroids considered while the infectious etiology is being determined. Restarting treatment with duvelisib is allowed after completion of the course of therapy and complete resolution of symptoms.

- Grade 3 or higher other nonhematologic toxicities including the following:
  - Infections: Subjects who develop infections requiring intravenous treatment with antibiotics/antifungals/antivirals should have duvelisib held until the infection resolves (subject may restart duvelisib when completing a course of oral therapy). Prophylaxis to prevent recurrent/opportunistic infections will not preclude the subject from restarting treatment.
  - Hepatic events: Subjects who develop Grade 3 or higher transaminase (ALT/AST) elevations with or without clinical symptoms should have duvelisib held until the values return to baseline. Duvelisib should be reintroduced after laboratory values have remained at baseline levels for at least 1 week. Additional work-up to evaluate viral infection/reactivation, exposure to environmental toxins (eg, alcohol/concomitant medications), or other causes is recommended before restarting treatment with duvelisib.

If ALT/AST elevations  $\geq$  Grade 3 recur upon rechallenge with duvelisib, hold duvelisib, and administer corticosteroids. A reduced dose of duvelisib may be reintroduced after laboratory values have remained at baseline levels for at least 1 week.

Any subject with new evidence of hepatitis B surface antigen seropositivity or other evidence of hepatitis B reactivation will be discontinued from duvelisib.

- Gastrointestinal (GI) events: In the setting of new or worsening Grade 2 GI events, early intervention is recommended to ameliorate risk of worsening symptoms. Subjects who develop Grade 3 or higher nausea, vomiting, or diarrhea despite optimal treatment should have duvelisib held until resolution of symptoms. Evaluation of concomitant medications, GI infections, or inflammatory bowel (via endoscopy and biopsy) should be considered with persistent diarrhea or recurrence with restarting duvelisib. As diarrhea induced by treatment with PI3K inhibitors has limited response to antimotility agents, early consideration of corticosteroid treatment is recommended.

If diarrhea  $\geq$  Grade 3 recurs upon rechallenge with duvelisib, hold duvelisib and administer oral corticosteroids. A reduced dose of duvelisib may be introduced after all symptoms resolve to baseline.

- Skin rash: Subjects who develop Grade 3 or higher skin rashes should have duvelisib held until resolution of symptoms. In the setting of new Grade 1 or 2 skin rash, early intervention is recommended to ameliorate risk of worsening symptoms. Evaluation of concomitant medications (eg, pneumocystis prophylaxis), environmental exposure, infections, or other contributing factors is recommended.

If rash  $\geq$  Grade 3 recurs upon rechallenge with duvelisib, hold duvelisib (also hold pneumocystis prophylaxis if not already done or other ongoing concomitant medications that may be contributing) and administer corticosteroids. A reduced dose of duvelisib may be reintroduced after all symptoms resolve.

- Cardiac: Subjects who develop new Grade 3 or higher cardiac events should have duvelisib held until resolution of symptoms. This includes new Grade 3 QT interval corrected with Fridericia's formula (QTcF) prolongation. A Grade 3 QTcF prolongation requires triplicate electrocardiograms with the average measurement used and the calculation of QTcF.

Where otherwise not specified, subjects requiring duvelisib treatment holds should be reevaluated at least weekly until the toxicity resolves according to the guidelines in [Table 4](#). Duvelisib dosing will be restarted at doses described in [Table 5](#).

### **7.3. Drug Accountability**

The Investigator or designee is responsible for taking an inventory of each shipment of investigational supplies received, and comparing it with the accompanying drug order form.

All unused duvelisib will be retained at the site. After full drug accountability and reconciliation, the Investigator will dispose of duvelisib at the clinical trial site according to site procedures or, at the Sponsor's request, will return all duvelisib to the Sponsor or its designee. If any duvelisib is lost or damaged, the disposition of duvelisib should be documented.

Subjects should be instructed to bring all used and unused duvelisib packaging to each study visit. The study site should count and document all capsules that the subject returns and should account for taken doses, missed doses, doses reduced due to missing or lost capsules, etc, before dispensing new duvelisib to the subject.

### **7.4. Assignment to Treatment**

All eligible subjects who are continuing treatment will receive duvelisib at the last dose level they were receiving in their previous study.

### **7.5. Assessment of Compliance**

At each applicable visit, duvelisib will be dispensed to the subject so that the subject will have enough doses until the next visit, taking into account the window for that subsequent visit. Compliance for doses taken outside of the clinic will be assessed by a count of the capsules returned to the study trial site by the subject and reviewed with the subject.

### **7.6. Treatment of Overdose**

Adverse events or SAEs associated with overdosage (intentional or unintentional) of duvelisib should be reported to the Sponsor as outlined in [Section 8.2.1.4](#).

In the case of overdose of duvelisib, clinic staff should be notified immediately and supportive care is to be given as indicated. Subjects should be informed to contact their doctor immediately

if they have taken an overdose and should stop taking duvelisib until further instructed by the treating physician or Investigator (or designee).

## 8. SAFETY DATA COLLECTION, RECORDING AND REPORTING

### 8.1. Adverse Events

#### 8.1.1. Definition of an Adverse Event

An AE is defined as any untoward medical occurrence in a patient or clinical investigation subject administered a pharmaceutical product and that does not necessarily have to have a causal relationship to this treatment.

An AE can, therefore, be any unfavorable and unintended sign (including an abnormal laboratory finding, for example), symptom, or disease temporally associated with the use of the medicinal product, whether or not considered related to the medicinal product.

Adverse events include worsening of a preexisting medical condition as well as clinically significant changes from baseline laboratory values or conditions. Worsening of the preexisting medical condition (eg, diabetes, hypertension) means that it has increased in severity, frequency, and/or duration, and/or has an association with a significantly worse outcome. A preexisting condition that has not worsened during the study is not considered an AE.

#### 8.1.2. Definition of Serious Adverse Event

An SAE is any untoward medical occurrence that at any dosage:

- Results in death
- Is immediately life-threatening
- Requires inpatient hospitalization or prolongation of existing hospitalization.
  - Elective or preplanned treatment for a preexisting condition that is unrelated to the indication under study and has not worsened since signing the ICF (as documented as medical history on the eCRF) is not considered an SAE
  - Scheduled therapy for the target disease of the study, including admissions for transfusion support or convenience, is not considered an SAE
- Results in a persistent or significant disability or incapacity
- Results in a congenital anomaly or birth defect
- Is considered an important medical event
  - If an AE does not meet 1 of the serious criteria, but the Investigator or Sponsor considers an event to be clinically important, the event could be classified as a SAE under the criterion of “Important medical event.” Examples of such medical events may include allergic bronchospasm requiring intensive treatment in an emergency room or at home or blood dyscrasias or convulsions that do not result in inpatient hospitalization.

## 8.2. Procedures for Eliciting, Recording, and Reporting Adverse Events

### 8.2.1. Eliciting and Recording Adverse Events

Subjects will be instructed to report all AEs and will be asked a general health status question at each study visit. All AEs occurring in eligible subjects will be recorded in the eCRF from the time the subject takes the first dose of duvelisib on this study (C1D1) through 30 days after the last dose of duvelisib. An AE will be followed until it is either resolved, has returned to baseline, or is determined to be a stable or chronic condition. All SAEs occurring from the signing of the ICF through 30 days after the last dose of duvelisib will be processed as outlined in [Section 8.2.2.](#)

At each required visit during the trial, all AEs that have occurred since the previous visit must be reviewed by the Investigator or designee. The Investigator or designee must determine if the AE is serious or nonserious.

The Investigator must assign the following AE attributes:

- AE diagnosis or syndrome(s) if known
  - If not known at time of the report, record the signs and/or symptoms as AEs and provide an updated report with diagnosis when obtained
- Dates of onset and resolution
- Severity as defined in this protocol
- Assessment of relatedness to duvelisib, and
- Action taken with duvelisib as a result of the AE

In general, an AE that is the primary cause of subsequent events should be identified by the primary cause (eg, for dehydration due to diarrhea, the AE would be diarrhea). However, AEs occurring secondary to an initiating event that are separated in time should be recorded as independent events (eg, sepsis secondary to pneumonia, both events should be recorded).

Progression of disease should not be reported as an AE/SAE but rather the signs and/or symptoms manifesting as the progression of disease should be reported (eg, for dyspnea due to progression of disease, the AE would be dyspnea). All fatal events must be reported as an SAE.

#### 8.2.1.1. Relationship to Study Drug

The Investigator must assess whether the AE may be related to duvelisib or study-mandated procedure, when applicable. The relationship is indicated by a 'yes' or 'no' response to the question: Is there a reasonable possibility that the event may have been caused by duvelisib or study procedure. A number of factors should be considered in making this assessment including:

1. the temporal relationship of the event to the administration of duvelisib or study procedure;
2. whether an alternative etiology has been identified;

3. mechanism of action of duvelisib; and/or
4. biological plausibility

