**Table 3: Disease Response Criteria**

| Disease type           | Examples of tumor assessment include:                          | Efficacy criteria                                 |
|------------------------|--|---|
| Lymphoma (except CTCL) | CT scan of chest, abdomen, and pelvis; FDG-PET where indicated | IWG criteria (Cheson et al, 2007)     |
| CTCL                   | Skin assessments   | mSWAT (Olsen et al, 2011)             |
| CLL                    | CT scan of chest, abdomen, and pelvis; complete blood count    | NCI-WG criteria (Hallek et al, 2008)  |

Abbreviations: CLL = chronic lymphocytic leukemia; CT = computed tomography; CTCL = cutaneous T-cell lymphoma; FDG = [F]fluorodeoxyglucose; IWG = International Working Group; mSWAT = modified Skin

Weighted Assessment Tool; NCI-WG = National Cancer Institute-sponsored Working Group; PET = positron emission tomography.

Note: Tumor assessments shown are examples and not necessarily comprehensive of the requirements needed for associated disease-specific efficacy criteria.

In this long-term extension study, a blinded central review of response assessments will not be performed. In addition, the following items are not required for investigator response assessments:

- Bone marrow biopsies and bone marrow aspirates, and
- Blood samples to determine minimal residual disease.

Adverse events, including SAEs, associated with any disease assessment must be collected as described in [Section 8.2](#).

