**Table 4: Dose Holds for Treatment-related Adverse Events**

| Treatment-related Toxicity a,b                              | Duvelisib c   |
|--|--|
| Hematologic   |  |
| ≥ Grade 3 FN   | Hold until afebrile and negative culture                                 |
| ≥ Grade 3 Thrombocytopenia with ≥ Grade 2 Hemorrhage                   | Hold until no evidence of hemorrhage and stabilization of platelet count |
| Other Grade 4 Hematologic Toxicity (excluding FN and Thrombocytopenia) | Continue   |
| Nonhematologic  |  |
| ≥ Grade 2 Pneumonitis/Pneumonia  | Hold until completion of course of therapy and resolution of symptoms    |
| ≥ Grade 3 Nonhematologic Toxicity                                      | Hold until ≤ Grade 1 or return to Baseline                               |

Abbreviations: AE = adverse event; CTCAE = Common Terminology Criteria for Adverse Events; FN = febrile neutropenia.

a Treatment-related AEs: possible, probable, or definite relationship to duvelisib.

b Toxicity grades are defined per CTCAE Version 4.03. Note if a parameter is not defined by CTCAE, then AE grading criteria ([Section 8.2.1.2](#)) should be utilized.

c Dosages of duvelisib may be reduced after subsequent occurrences of the same treatment-related AE. See [Section 7.2.1](#) for more information on dosing modification and discontinuation.

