#### 8.2.2. Reporting of Serious Adverse Events

A SAE Report Form will be completed and submitted to the Sponsor or designee within 24 hours of the Investigator's first knowledge of the event, even if the experience does not appear to be related to duvelisib, from the time the subject signs the ICF through 30 days after the last dose of duvelisib. Please refer to the SAE Report Form for where and how to submit the form.

The initial SAE report form must be as complete as possible, including details of the current illness and (serious) AE, and an assessment of the relationship between the event and duvelisib. Additional information relating to a previously reported SAE must also be reported within 24 hours of the Investigator's first knowledge of information. The Investigator may also be asked, by the Sponsor, to provide clarifications or additional information. If the Investigator becomes aware of an SAE, considered related to duvelisib by the Investigator, occurring more than 30 days after the last dose of duvelisib, the SAE must be reported as described above.

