7.3 Safety Analyses

7.3.1 Adverse Events

Adverse events will be coded using MedDRA Version 19. The Grade of the AE will be assessed according to the NCI-CTCAE Version 4.03. If an AE is not included in the NCI-CTCAE Version 4.03, the Grade of the AE will be assessed according to the protocol, Section 8.2.1.2.

The summary of AEs will be focused on treatment-emergent AEs. Since this is an extension study, a treatment-emergent AE (TEAE) is defined as any AE that is reported out to 30 days after the last dose of study treatment. The onset date of an AE will be compared to the last dose date plus 30 days to determine whether the AE is treatment-emergent or not.

TEAEs will be summarized for each treatment arm by MedDRA system organ class (SOC) and preferred term (PT), or PT only. For summary tables by SOC and PT, SOC will be sorted alphabetically and PT will be sorted by decreasing frequency in the duvelisib arm within each SOC. For summary tables by PT only, PT will be sorted by decreasing frequency in the duvelisib arm.

If multiple TEAEs of the same PT occur within a subject, only the maximum grade observed for this PT will be used in summary of TEAEs by grade, the subject will be counted only once in the number of subjects for this PT and only once for the number of subjects for the SOC to which this PT belongs.

An overview TEAE summary table will be provided, which will include the number of subjects with AEs in selected categories. In addition, TEAEs will be summarized for the following categories, and will be tabulated by SOC and PT, unless otherwise specified.

- Treatment-emergent AEs
- Treatment-emergent AEs related to duvelisib
- Treatment-emergent AEs leading to treatment discontinuation
- Treatment-emergent AEs by maximum grade
- Grade 3 or higher treatment-emergent AEs
- Treatment-emergent SAE
- Treatment-emergent SAE related to duvelisib

Adverse events of special interest (AESI) will be summarized overall and with grading specifications. The AESI categories and associated PT's are provided in Appendix A of this document.

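### The protocol's single causality question joins duvelisib and study procedures, while the safety tables report events related to duvelisib alone and no rule connects the two

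*Protocol*

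**What the plan says.** Protocol 8.2.1.1, headed as the relationship to study drug, is the only place that tells the investigator how to record causality. It opens with "The Investigator must assess whether the AE may be related to duvelisib or study-mandated procedure, when applicable" and continues: "The relationship is indicated by a 'yes' or 'no' response to the question". The question is "Is there a reasonable possibility that the event may have been caused by duvelisib or study procedure".

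Two neighbouring sections name the drug only. The attributes that the investigator must assign under Protocol 8.2.1 include "Assessment of relatedness to duvelisib, and" the action taken with the drug because of the event. Protocol 8.2.2 requires the initial SAE report to contain "an assessment of the relationship between the event and duvelisib".

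The dose-hold rules use graded terms. Protocol 7.2 sets the threshold at an event at least possibly related to duvelisib. Footnote a of Table 4 reads "Treatment-related AEs: possible, probable, or definite relationship to duvelisib".

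On the analysis side, Protocol 9.4 plans separate summaries of TEAEs and of serious TEAEs related to duvelisib. SAP 7.3.1 lists "Treatment-emergent AEs related to duvelisib" and the corresponding SAE table. Neither section defines related or names the field from which it is derived.

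**The concern.** AEs are a primary endpoint, and the study is open-label with no randomised control. The investigator's attribution is therefore the main causality information that a reader of the related-event tables will have. Those tables should contain events attributed to the drug.

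The only recording instruction produces an answer that does not isolate the drug. An investigator who follows Protocol 8.2.1.1 to the letter must answer yes for a reaction caused solely by a scan or a blood draw, and the yes does not show which cause was meant. If that answer supplies the flag for the tables, they mix two kinds of event under a label that names one. The same answer could also bear on the regulatory notification of serious, unexpected and related events in Protocol 8.2.2.2.

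**Working it through.** The documents give no figure to reproduce. The check sets the passages side by side and then works out the direction of any error.

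**Which cause is named, and on what scale**

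- Protocol 8.2.1.1: drug or procedure; yes/no; one question.
- Protocol 8.2.1 (AE attributes): drug only; no scale given.
- Protocol 8.2.2 (SAE report): drug only; no scale given.
- Protocol 7.2 and Table 4 footnote a: drug only; possible, probable or definite.
- Protocol 9.4 and SAP 7.3.1: drug only; no derivation given.

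Four of the five refer to the drug alone. The fifth, the only one that says how the answer is obtained, joins the drug to a procedure. SAP 8.1 lists only the adverse events of special interest as a change from the protocol, so it does not settle the matter.

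**Are procedure-caused events in the data?** Yes. After Table 3, Protocol 6.2.6 states "Adverse events, including SAEs, associated with any disease assessment must be collected". Table 1 schedules laboratory tests every 84 days while on treatment, which is 365/84 = about 4.3 times a year, with radiologic evaluation once a year.

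**Direction of the error.** For any row of a related-event table, let D be the subjects with an event in that row attributed to duvelisib, P those with an event in that row attributed to a procedure, and N the size of the All-Treated Analysis Set.

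- Drug-only flag: the count is |D|.
- Combined flag: the count is |D or P| = |D| + |P not D|.
- Excess: |P not D|, which is zero or more. In percentage points it is 100 × |P not D| / N.

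The related count can therefore only stay the same or rise. In the row for any related TEAE, a subject with both kinds of event adds nothing. In a preferred-term row, a subject adds to the excess if the procedure caused that term and the drug did not.

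**Size.** The documents give neither |P not D| nor N, so the excess cannot be calculated. The visit frequency of 4.3 a year shows only how often a procedure-caused event could arise; it is not a rate of such events. Protocol 6.2.6 does not require bone marrow biopsies or aspirates for response assessment. The scheduled procedures are thus mainly blood draws and a yearly scan, which points to a small effect.

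**The scales.** Possible, probable and definite are treated alike in Table 4, so together they act as a yes/no threshold. That threshold is probably close to a reasonable possibility, but no sentence says that the two are the same.

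**The case against.** The strongest reply is that the drug-only assessment already exists. Protocol 8.2.1, directly above the disputed section, lists relatedness to duvelisib as a required attribute. Protocol 8.2.2 asks for it on the SAE report, and the planned tables match both. The qualifier on applicability in 8.2.1.1 leaves room for separate form items, and the forms are not among the documents. This stands as far as it goes. A reader might infer that procedure-caused events *are* counted as related to duvelisib. The documents do not support that, because no passage makes the combined answer the analysis flag. What remains is that 8.2.1 and 8.2.2 require a drug-only attribute without saying how to obtain it, and the one section that does gives a joint question.

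A reader might also infer that related events cannot be matched to dose holds. That does not follow. Protocol 8.2.1 records the action taken with duvelisib for each AE, which links a hold to its event on any causality scale. SAP 7.1.3 counts subjects with a hold and plans no cross-tabulation with relatedness.

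The effect on SAE reporting is limited too. Under Protocol 8.2.2, every SAE through 30 days after the last dose is reported whatever its cause, and the later trigger names the drug alone. Medical events of interest are reported regardless of relationship. The summaries of all TEAEs, Grade 3 or higher TEAEs, serious TEAEs and events of special interest do not use causality at all.

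**Conclusion.** The point holds in a limited form. Protocol 8.2.1.1, followed literally, yields an answer that cannot separate the drug from a procedure, and neither the protocol nor the SAP says which answer defines related to duvelisib. This is more than missing detail, because the stated rule can give a wrong classification.

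The consequence is conditional. If the combined answer is the flag, procedure-only events can enter the TEAE and serious TEAE tables labelled as related to duvelisib, and counts can only stay the same or rise. A percentage-point figure is tempting, but with no rate in the documents it would merely restate whatever rate was assumed. The effect is probably small, given the mostly routine procedures and a study for which SAP 3.5 plans no inferential analysis. If the form already records the two causes separately and the drug item feeds the tables, the counts are right and only the wording needs correcting.

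The difference between the graded terms of the hold rules and the yes/no item is real but secondary, and mostly one of vocabulary.

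**What to change.** - In Protocol 8.2.1.1, replace the joint question with two yes/no questions: one on relatedness to duvelisib and one on relatedness to a study-mandated procedure. Make the same change on the AE and SAE forms if they do not already separate the two.
- In SAP 7.3.1, state that related to duvelisib means yes to the first question.
- Reconcile the graded terms in Protocol 7.2 and Table 4 footnote a with the yes/no item in 8.2.1.1, so that it is clear how they correspond. Which threshold should govern holds is a clinical matter for the sponsor.

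The cost is a small wording change in each document and possibly one extra form field. If the form holds only the combined answer, the cause behind each recorded yes can be recovered only by querying sites, so an early change is cheaper.
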